8.3.11 Laboratory Evaluations

During the study, blood samples will be drawn for screening, safety and research purposes. The blood sampling schedule in the flowchart (section 8.3.18) shows the maximum amounts of blood that will be drawn. Following universal precautions, blood will be collected by venipuncture into vacutainer tubes. Blood specimens will be affixed with coded labels that link the specimen to the subject, specimen type, specimen collection date, and time-point. The specimen collection tube must be appropriate for the type of specimen required. The cumulative blood draw for each subject over the entire course of study participation is approximately 400mL.

Biological safety parameters will be measured on plasma or serum samples at the central laboratory of the RUMC. In the case where a laboratory assessment is outside the reference range, a decision regarding whether the result is of clinical significance or not shall be made by the investigator and shall be based, in part, upon the nature and degree of the observed abnormality. The assessment may first be repeated for confirmation. All abnormalities will be documented in the source documents, including clinical considerations.

Pharmacokinetic and functional analysis of transmission reduction activity

Pharmacokinetic (pK) sampling will establish the dose-response curve for each subject enrolled in this Phase 1 study. The serum concentrations of TB31F will be measured by an ELISA against a recombinant epitope R0.6C of the Pfs48/45 antigen at each sampling time point. Assessment of TB31F concentrations in the serum from subjects will be performed by the Human Immunology Laboratory at Imperial College London. Functional transmission-blocking activity will be determined at defined intervals as per protocol using SMFA assays performed at Radboudumc in Nijmegen the Netherlands

Complete Blood Count (CBC)

Complete hematology tests, including hemoglobin, hematocrit, red blood cell count, white blood cell count with differential (including neutrophils, basophiles, eosinophils, monocytes and

lymphocytes) and platelet count will be measured when appropriate. Complete hematology will be done at screening, at inclusion, at 24 hours and days 2, 7, 14, 21, 28 and 84.

Clinical Chemistry

Glucose will be measured only at screening. Alanine aminotransferase (ALT), aspartate aminotransferase (AST), creatinine, will be measured at screening, inclusion, at 24 hours and days 2, 7, 14, 21, 28 and 84.

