8.3.17 Safety Assessments

Planned safety assessments will provide the data for active monitoring of investigational product safety during conduct of the trial and for the primary reactogenicity and safety endpoints. Subjects will be observed directly for 60 minutes following product administration. AEs will be recorded prior to infusion, EOI, 6 and 24 hours, and at all follow-up visits. Clinical laboratory results assessed as AEs will be scored for severity using adapted Food and Drug Administration Toxicity Tables (see Appendix 1).

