9.5.3 Review of safety data by the safety monitor and SMC

Safety Meetings

The SMC will review safety data at pre-defined time points throughout the study, specifically: upon completion of ≥ 7 days of post-administration follow-up in all subjects in a given dose-group (prior to commencing the first administration in the subsequent dose group). The chair of the SMC will determine for each time point whether a meeting will be held, or whether a recommendation from all members may be formalized through e-mail. The frequency of these reviews may be adapted upon SMC recommendation if deemed necessary. In addition, safety data for all participants will be assessed by the SMC at the end of the study. An ad hoc SMC meeting may be convened at any time or at the request of the PI or local safety monitor to review safety data from subjects and/or groups who meet any of the holding rules as specified in the protocol (9.5.4) and SMC charter.

Safety Reports

Safety reports will be prepared by the clinical investigator for review by the committee prior to each review. These reports will provide at a minimum the following information:

- Accrual data and subject status data with regard to completion of/discontinuation from the study.
- Summaries of solicited AEs, classified by severity.
- Unsolicited AEs (including SAEs), categorized by ICD-10 coding, severity and relatedness to study vaccine.
- Safety laboratory test results outside of normal institution reference ranges and considered clinically significant, classified by severity grading scale (irrespective of whether assessed as AEs).
- Any new or updated AEs that have met the holding rules.

The SMC will review the safety data within 2 working days. The SMC will summarize their recommendations to the study Sponsor as to whether there are safety concerns and whether the study should continue without change, be modified, or be terminated. If at any time a decision is made to permanently discontinue administration of study TB31F administrations in all subjects, the Sponsor will notify the METC and PATH expeditiously.

The advice(s) of the SMC will only be sent to the Sponsor of the study. Should the Sponsor decide not to fully implement the advice of the SMC, the Sponsor will send the SMC advice to the METC, including a note to substantiate why (part of) the advice of the SMC will not be followed.

Within-group progression

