#### Safety outcome measures:

1. Number and severity of solicited local adverse events from the moment of first product administration through day 7
2. Number and severity of solicited general AEs from the moment of first product administration through day 28
3. Number and severity of clinically significant hematological and biochemical laboratory abnormalities from the moment of first product administration through day 28
4. Number and severity of unsolicited adverse events from first product administration through end of study
5. Number of serious adverse events from first product administration through end of study

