|               | Grade 2   |           |   |           |   |           |   |           |   |           |   |           |   |
|               | ...       |           |   |           |   |           |   |           |   |           |   |           |   |
|               | ....      |           |   |           |   |           |   |           |   |           |   |           |   |
| Any local AE* | Grade 1   |           |   |           |   |           |   |           |   |           |   |           |   |
|               | Grade 2   |           |   |           |   |           |   |           |   |           |   |           |   |
|               | Grade 3   |           |   |           |   |           |   |           |   |           |   |           |   |
|               | Any grade |           |   |           |   |           |   |           |   |           |   |           |   |
|               |           |           |   |           |   |           |   |           |   |           |   |           |   |
| Systemic AE1  | Grade 1   |           |   |           |   |           |   |           |   |           |   |           |   |

|                 |         |  |  |  |  |  |  |  |  |  |  |  |  |
|-----------------|---------|--|--|--|--|--|--|--|--|--|--|--|--|
|                 | Grade 2 |  |  |  |  |  |  |  |  |  |  |  |  |
|                 | ...     |  |  |  |  |  |  |  |  |  |  |  |  |
| Any general AE* | Grade 1 |  |  |  |  |  |  |  |  |  |  |  |  |
|                 | Grade 2 |  |  |  |  |  |  |  |  |  |  |  |  |
|                 | ...     |  |  |  |  |  |  |  |  |  |  |  |  |
|                 |         |  |  |  |  |  |  |  |  |  |  |  |  |
| Any AE*         | Grade 1 |  |  |  |  |  |  |  |  |  |  |  |  |
|                 | Grade 2 |  |  |  |  |  |  |  |  |  |  |  |  |
|                 | ...     |  |  |  |  |  |  |  |  |  |  |  |  |

\* List (only) highest grade AE per subject

Clinical Laboratory Data Analysis

- All clinical laboratory abnormalities will be analyzed by participant and will include details of onset time, duration, severity and relationship to the study infusion dose (outcome measure 3).
- Any clinically significant deviations in routine laboratory test results, as determined by the investigator, will be summarized per group (outcome measure 3).
- Isolated laboratory abnormalities will be reported as unsolicited AEs if they are considered clinically relevant by the investigator.

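### The per-group laboratory summary and the minimum laboratory content of the SMC report hold only results the open-label investigator judges clinically significant; no table by grade and group, and no shift from the inclusion value, is planned.

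*SAP*

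**What the plan says.** The SAP's Safety outcome measures define the laboratory endpoint as "Number and severity of clinically significant hematological and biochemical laboratory abnormalities from the moment of first product administration through day 28". Two consecutive bullets under Clinical Laboratory Data Analysis then say how it is analysed:

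- By participant: "All clinical laboratory abnormalities will be analyzed by participant and will include details of onset time, duration, severity and relationship to the study infusion dose".
- By group: "Any clinically significant deviations in routine laboratory test results, as determined by the investigator, will be summarized per group".

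Protocol 8.3.11 says who decides about an out-of-range result: "a decision regarding whether the result is of clinical significance or not shall be made by the investigator". The same section keeps the full record at source: "All abnormalities will be documented in the source documents, including clinical considerations". Protocol 8.2 states that the trial is open-label.

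On grading, Protocol 8.3.17 says: "Clinical laboratory results assessed as AEs will be scored for severity using adapted Food and Drug Administration Toxicity Tables". Table A4 in Appendix 1 gives numeric limits for grades 1 to 3 for haemoglobin, leukocytes, platelets, creatinine, AST and ALT.

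For the SMC, the laboratory item in the minimum report content of Protocol 9.5.3 is "Safety laboratory test results outside of normal institution reference ranges and considered clinically significant". These results are then classified by grade whether or not they were recorded as AEs. The inter-group progression paragraph of 9.5.3 and Protocol section 3 also refer to clinically significant laboratory tests on days 1, 2 and 7. Protocol 10.1 plans a listing of deviations that the investigator considers clinically important.

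**The concern.** Solicited AEs get a full SAP table: each grade, each group, counts and percentages. Laboratory values, which have a more objective scale, do not. Their group display passes first through a case-by-case judgement by someone who knows the dose, and the documents set no grade at which a result must count as significant.

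A modest rise in transaminases or a modest fall in a cell count, shared by several subjects in one group, is the pattern that such a filter can remove. Each value may reasonably be called unimportant alone; the information lies in the group pattern. If the values are not called significant, the pattern is missing from the group summary and from the minimum package on which the SMC advises. Blood count and chemistry are taken at inclusion and on days 1, 2, 7, 14, 21 and 28, so the data for a graded display with a baseline already exist. The plan does not use them in that way.

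**Working it through.** **1. Where the filter applies**

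| Display | Restricted to results judged clinically significant or important? | Rate by grade and group? | Shift from inclusion? |
|---|---|---|---|
| SAP, by-participant bullet | No (all abnormalities) | No | No |
| SAP, per-group bullet | Yes | Not specified | No |
| Protocol 10.1 listing | Yes | No | No |
| Protocol 9.5.3 SMC report, minimum content | Yes, then graded | Not specified | No |

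The by-participant bullet escapes the filter on its plain wording. Two things leave it uncertain: it is tagged to outcome measure 3, which is limited to clinically significant abnormalities, and Protocol 8.3.17 provides severity scoring only for laboratory results assessed as AEs.

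**2. The plan's own detection figures** (Protocol 4.4; SAP, Sample size), n = 20

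- At least one event at a true rate of 10.87%: 1 − (1 − 0.1087)^20 = 0.900. Stated: 90%.
- No event at a true rate of 0.52%: (1 − 0.0052)^20 = 0.901. Stated: 90%.

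Both reproduce. They presume that every event is counted. Let q be the share of graded laboratory changes that the investigator calls significant. The documents give no value for q, so a range is shown. The chance that the filtered count shows at least one laboratory event at a 10.87% rate is 1 − (1 − 0.1087q)^20:

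- q = 1: 90.0%
- q = 0.75: 81.8%
- q = 0.5: 67.3%
- q = 0.25: 42.4%
- q = 0.1: 19.6%

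**3. Chance that a group of five shows zero**

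Let r be the true proportion of subjects with a graded change (assumed), with judgements independent. Then P(0 of 5) = (1 − rq)^5, against (1 − r)^5 if every graded value counts.

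| r | q = 0.1 | q = 0.25 | q = 0.5 | All graded values count |
|---|---|---|---|---|
| 0.6 | 0.94^5 = 73% | 0.85^5 = 44% | 0.70^5 = 17% | 0.4^5 = 1% |
| 0.4 | 0.96^5 = 82% | 0.90^5 = 59% | 0.80^5 = 33% | 0.6^5 = 8% |

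**4. The extreme case**

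If all five subjects have a graded change, the group shows 0/5 with probability (1 − q)^5: 59.0% at q = 0.1, 23.7% at q = 0.25 and 3.1% at q = 0.5. It is certain only at q = 0. The exact 95% interval for 0/5 runs up to 1 − 0.025^(1/5) = 52.2%; for 5/5 it starts at 0.025^(1/5) = 47.8%.

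**The case against.** The strongest reply is that nothing is hidden. The SAP bullet just before the group summary covers all abnormalities by participant, with severity and relationship to dose, and with five subjects per group a reader could see a shift there. This stands. A reader might infer that results are filtered before any grading takes place, or that a shift would be reported as zero throughout the trial. The documents do not support either reading. What the bullet does not supply is a rate by grade and group, or a route to the SMC.

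A reader might also infer that the SMC cannot see other laboratory results. That too goes beyond the text. The 9.5.3 list is a minimum, AE status is no gate to grading in it, Protocol section 3 speaks more generally of the laboratory data available, and the SMC charter is not among the documents. The supportable statement is that unfiltered results are not guaranteed to reach the SMC.

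Nor is baseline ignored: Protocol 9.2.2 treats significant worsening of a clinically significant baseline finding as reportable. But this is again a judgement about AE reporting, not a planned shift analysis.

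The numbers can be attacked because r and q are assumed. That stands, and nothing shows that this investigator would under-call rather than over-call. Independence is a further assumption, although it is not the unfavourable one. If one person's threshold applied to the whole group, all or none with equal chance, the probability of zero at r = 0.6 would be 0.5 + 0.5 × 0.01 = 51%, not 17%.

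Finally, restricting the endpoint to clinically significant abnormalities is declared consistently in both documents. That makes it a legitimate endpoint, but not a sufficient sole group display.

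**Conclusion.** The point holds for two displays: the SAP's per-group laboratory summary and the minimum laboratory content of the SMC report. Both depend on an unblinded judgement with no link to Table A4, and neither is accompanied by a grade-by-group or shift table. A consistent low-grade change in one dose group can therefore be missing from both, while remaining visible in the by-participant analysis.

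The size cannot be derived from the documents. At an assumed 60% rate of graded change, with 10% to 50% called significant, the group summary shows zero with probability 73% to 17%, against 1% unfiltered. These figures describe the group display alone, not everything that the trial reports. It is a modest weakness in a descriptive study, but it affects part of the primary safety endpoint and is cheap to remove.

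**What to change.** - **SAP, Clinical Laboratory Data Analysis:** add a per-group table of worst post-dose Table A4 grade through day 28, and shift from the inclusion value, regardless of investigator judgement. Limit the grading to the analytes that have Table A4 limits (haemoglobin, leukocytes, platelets, creatinine, AST, ALT). Show the other measured analytes, such as bilirubin, LDH and hs-Trop-T, against reference ranges. Keep the clinically significant summary as a second display.
- **Protocol 9.5.3:** include the same table in the SMC report. Protocol 13.2 records that groups 1 to 4 have been dosed, so this can serve only a review still to come and the end-of-study assessment. The SAP table would still cover all 25 subjects.
- **Protocol 8.3.17 and 10.1:** reconcile both with the SAP bullet on all abnormalities, so that it is clear which results are graded and which are listed.

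The cost is a short protocol and SAP wording change and one more table; no new samples. More grade 1 entries will appear, so the reported abnormality rates may look less favourable.

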**Efficacy outcome analyses:**

- TB31F antibody prevalence and density will be determined by ELISA; the mean of duplicate concentration estimates is used for analyses. Antibody density will be expressed in µg/mL (outcome measure 6).
- TB31F antibody density will be plotted over time per individual and either as a mean or geometric mean per group. Mixed effects models may be used to investigate the interaction of timepoints and group on TB31F antibody concentration, allowing for subject specific random intercepts to control for the correlation within individuals (outcome measure 6).
- TB31F pharmacokinetics will be analyzed using standard non-compartmental methods to establish the maximum concentration ( $C_{max}$ ), terminal half-life ( $t_{1/2}$ ), area under the curve (AUC  $0-\infty$ ) and Volume of Distribution ( $V_d$ ) for each subject who received mAb TB31F. Additionally, the absorption rate constant ( $K_a$ ) will be determined for group 5 (subcutaneous administration). Geometric mean and geometric coefficients of variation of  $T_{1/2}$  and  $V_d$ , as well as of dose-adjusted  $C_{max}$  and AUC will be reported per dose group and overall (outcome measure 7).
- TRA will be quantified as the relative reduction in oocyst intensity for test samples (one feeder per test sample) compared to pooled naïve serum controls (two feeders). Samples may be tested in one or two independent SMFA experiments. TRA values for each participant and time-point will be estimated using generalized linear models, as previously described (outcome measure 8).

- We may calculate the percentage of individuals per group that have at least 50%, 80% and 90% TRA per timepoint and the percentage of individuals per group with statistically significant TRA at each timepoint. Mean TRA levels may also be calculated per study group per time point and compared between groups (outcome measure 8).
- The precision of TRA estimates by SMFA decreases with decreasing TRA. Samples with lower levels of TRA (typically below 80%) may thus have relatively imprecise TRA estimates. For some analyses, we may thus use TRA estimates that are inferred from antibody concentration based on the best fit model for the association between antibody concentration and TRA. For this fit, we will use mixed effects models, similar to methods described by Miura et al., adjusting TB31F antibody concentrations measured in serum to reflect whole blood concentrations. These models will be used to find the best fit model for the association between TB31F antibody concentration and TRA and to estimate Inhibitory Concentration values (e.g. IC80, IC50) (outcome measures 7, 8).

Modeled TRA estimates (based on antibody concentration) will be plotted against observed TRA estimates (outcome measure 8).

- TBA will be quantified as the reduction in oocyst prevalence in the presence of test serum as compared to control serum^1 and presented per group and time-point (outcome measure 9).
- The obtained pharmacokinetic and pharmacodynamic data will be further analyzed integrally by means of non-linear mixed effects modeling (outcome measure 7, 8). Using an exploratory approach, we will fit single and multicompartmental methods to the obtained pharmacokinetic data and investigate both linear and non-linear elimination and disposition. Thereafter, we will investigate whether the pharmacokinetics relate with TRA. The developed pharmacokinetic-pharmacodynamic model will be used for *in silico* exploration of:
  - o TB31F dosing regimens needed to achieve at least 80% TRA during an epidemiological relevant time frame (e.g. a typical transmission season of three months)
  - o the effect of monoclonal antibody engineering, resulting in a longer circulation half-life due to a more favorable pH-dependent binding to human neonatal receptor on the dose needed to achieve at least 80% TRA during an epidemiological relevant time frame (e.g. a typical transmission season of three months)
  - o the effect of subcutaneous administration on the dose needed to achieve at least 80% TRA during an epidemiological relevant time frame (e.g. a typical transmission season of three months)

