recommended by the US FDA Maximum Recommended Starting Dose (MRSD) guidelines using a rat preclinical model. Sub-optimal (i.e., <80%) TRA (MABEL) is first detectable in SMFA between 1-2 μ g/mL. A dose of 0.1 mg/Kg TB31F administered to 60 kg volunteer with a circulating volume of 5 L, would be expected to result in a peak concentration of ~1.2 μ g/mL. Note that this approach results in a starting dose ~40-fold lower than that calculated using MRSD guidelines, based on the maximum dose of 240 mg/kg of TB31F tested in rat preclinical toxicity study in which no observed adverse effect levels (NOAELs) were observed in the tested rat species. This NOAEL of 240 mg/kg was used to convert to the Human Equivalent Dose (HED). $HED = NOAEL_{rat} \text{ of } 240 \text{ mg/kg} * 0.16 = 38.4 \text{ mg/kg}$ assuming a 0.23 kg rat and a 60 kg human. The default safety factor that should normally be used is 10-fold. The HED calculation resulted in 3.84 mg/kg. The proposed starting dose of 0.1 mg/kg in Group 1 is thus approximately 40 times lower than the calculated HED.

- 3) We selected a range of four concentrations based on dose escalation from the initial dose of 0.1 mg/kg to the highest dose of 10 mg/kg in order to provide meaningful separation of exposure between dose groups for safety evaluation of adverse events and for PK assessment of monoclonal antibody concentration over time. A model-based meta-analysis of monoclonal antibody pharmacokinetics of groups receiving different dosages was used to estimate serum concentrations following TB31F infusion over time.

[figure not shown]

Figure 8 – Pharmacokinetic properties of monoclonal antibodies administered at 1 to 30 mg/kg

Based on known functional activity of TB31F serum concentrations in SMFA, we predict detectable TRA will be observed in all groups administered TB31F mAb at peak concentration following administration and >80% TRA (that corresponds with blocking activity) will be achieved in the four highest dose groups. By the end of the study (day 84), we would predict that subjects in groups receiving the highest dosage of TB31F (10 mg/kg) would still exhibit transmission blocking activity while subjects in Groups 1 and 2 that were administered TB31F at 0.1 and 1 mg/kg would no longer demonstrate inhibitory activity.

We chose a broad range of dosages to answer critical questions with respect to the functional in vivo functional properties of TB31F:

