13.2 Update of risk assessment for amendment v1.6 (prior to group 5)

Following TB31F administration in groups 1-4, the following update of the risk assessment can be made:

a. Level of knowledge about mechanism of action

TB31F has been administered intravenously to n=20 subjects in groups 1-4. No ADA have yet been measured.

b. Previous exposure of human beings with the test product(s) and/or products with a similar biological mechanism

TB31F has been administered intravenously to n=20 subjects in groups 1-4. Administration is safe and well-tolerated at all administered doses including in the 5 volunteers at the highest dose of 10mg/kg. There have been no grade 3 AEs or SAEs for any of the dosage groups. Two out of 20 volunteers reported local solicited adverse events, both grade 1. The most common general solicited adverse event was grade 1 or 2 fatigue on day of TB31F administration in 12 out of 20 volunteers. Fatigue is a known side-effect of the pre-medication clemastine. TB31F has not previously been administered intradermally, subcutaneously or intramuscularly.

c. Can the primary or secondary mechanism be induced in animals and/or in ex-vivo human cell material?

No change.

d. Selectivity of the mechanism to target tissue in animals and/or human beings

No change.

e. Analysis of potential effect

Preliminary analysis shows that there is a TRA of approximately 50% in group 1 (0.1 mg/kg) at end of infusion. In group 2 (1 mg/kg), TRA of >95% is maintained up to day 28 after TB31F administration.

f. Pharmacokinetic considerations

The pharmacokinetic evaluation in human subjects will be analyzed from human sera collected at several time points after TB31F administration. See time and event table for details. Preliminary analysis of TB31F concentrations in serum over time indicate a half-life of approximately 20.5 days, in line with other human IgG1 molecules.

g. Study population

No change.

h. Interaction with other products

No change.

i. Predictability of effect

Preliminary analysis of the SMFA in group 1 (0.1mg/kg) show a TRA of approximately 50% at end of infusion. With the dosage of group 2 (1mg/kg), a TRA of more than 95% was maintained up to day 28 after administration.

The subcutaneous dosage of 100 mg mAb TB31F is predicted to have >80% inhibition of the development of oocyst stage parasites in the mosquito with >80% 28 days after administration.

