## Introduction

TB31F is a first-in-human phase I, open-label, single-site, dose-escalation study to determine the safety, tolerability and pharmacokinetics of the monoclonal antibody (mAb) TB31F. MAb TB31F will be administered intravenously (i.v.) (groups 1-4) or subcutaneously (group 5) as a single dose to 25 healthy adults, 5 groups of 5 volunteers. The study participants are followed for a 12-week period after infusion; samples are collected following a scheme defined in the study protocol.

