#### Efficacy outcome measures:

6. TB31F mAb concentration in serum at different time-points post administration
7. Pharmacokinetic parameters of the TB31F mAb determined by non-compartmental analysis (e.g. maximum concentration ( $C_{max}$ ), terminal half-life ( $t_{1/2}$ ), area under the concentration versus time curve (AUC), volume of distribution ( $V_d$ ) and the absorption rate constant ( $K_a$ ) when TB31F is administered subcutaneously)
8. Transmission reducing activity (TRA) of participant serum at different time-points post administration, quantified as percentage reduction of oocyst densities in the presence of test serum as compared to control serum in standard membrane feeding assays (SMFA)
9. Transmission blocking activity (TBA) of participant serum at different time-points post administration, quantified as percentage reduction in oocyst prevalence in the presence of test serum as compared to control serum in standard membrane feeding assays (SMFA)

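### The optional timepoint-by-group model for TB31F concentration names only subject random intercepts; on log concentration in the IV groups, this makes its interaction test anti-conservative when half-life varies between subjects

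*SAP*

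**What the plan says.** For outcome measure 6 ("TB31F mAb concentration in serum at different time-points post administration"), the SAP's efficacy outcome analyses state: "Mixed effects models may be used to investigate the interaction of timepoints and group on TB31F antibody concentration", and continue "allowing for subject specific random intercepts to control for the correlation within individuals". Neither document gives this model a random slope, a serial covariance or a small-sample degrees-of-freedom method.

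The scale is not fixed. The plotting sentence reads "TB31F antibody density will be plotted over time per individual and either as a mean or geometric mean per group", and the Statistical Principles section allows a transformation for non-normal outcomes. The groups are not restricted either. TB31F is "administered intravenously (i.v.) (groups 1-4) or subcutaneously (group 5) as a single dose to 25 healthy adults", so group could mean all five.

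The general significance level is 0.05. The SAP's sample-size section says that the study is not specifically powered for comparisons between arms.

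Elimination is also covered elsewhere. The SAP says "TB31F pharmacokinetics will be analyzed using standard non-compartmental methods to establish the maximum concentration", terminal half-life and other parameters for each subject, with geometric means and geometric CVs of half-life per dose group. It also plans exploratory non-linear mixed-effects modelling of linear and non-linear elimination.

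**The concern.** A random intercept lets each subject's log-concentration profile sit higher or lower, but within a group it forces the profiles to be parallel. Subjects with different half-lives do not have parallel profiles: the profiles fan out over 84 days. The SAP expects such variation, since it plans to report a CV of half-life per group.

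Under the named model this fanning goes into the residual and is counted as independent noise at every sample. The interaction test then claims far more information than 5 subjects per group supply. A significant p-value from it could not, taken alone, be told apart from ordinary variation in half-life between subjects.

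The open choice of scale and groups adds a separate problem of interpretation. In some permitted versions the interaction is real even when every subject eliminates the antibody at the same rate.

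**Working it through.** The plan states no figure for this model beyond the 0.05 level, so there is none to reproduce.

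**Inputs from the documents.** Four IV groups of 5. Twelve post-dose PK times (protocol 8.3.18): end of infusion, 1, 3, 6 and 24 h, days 2, 7, 14, 21, 28, 56 and 84. Half-life from protocol 13.2: "Preliminary analysis of TB31F concentrations in serum over time indicate a half-life of approximately 20.5 days".

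**Assumed, because the documents give no variances.** Half-life CV 0, 10, 20 or 30% (lognormal, median 20.5 days); residual CV 10, 15, 25 or 35%; intercept CV 20%; complete data.

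**Size of the fanning.** The elimination rate is ln 2 / 20.5 = 0.0338 per day. By day 84 the mean log decline is 0.0338 × 84 = 2.84. The SD between subjects from half-life alone is roughly CV × 2.84, that is 0.28, 0.57 and 0.85 at CV 10, 20 and 30%. The residual SD on the log scale is roughly 0.10 to 0.35.

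**Why the test goes wrong.** With balanced data and categorical time, the random-intercept interaction test is the split-plot F on (4−1)(12−1) = 33 and 4 × (5−1) × (12−1) = 176 df. Under the null, numerator and denominator have the same expectation; the degrees of freedom are what is wrong. If slope differences made up all the subject-by-time variation, the statistic would follow F on 3 and 16 df but be compared with the 5% critical value for 33 and 176 df, which is 1.50. P(F(3,16) > 1.50) = 25%, so inflation in this version approaches a ceiling of about 25%.

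**Simulated type I error** (same median half-life in all groups, log scale, IV groups 1-4, categorical time, 20,000 trials per cell; repeat runs agree within one percentage point):

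| Half-life CV | Residual CV 10% | 15% | 25% | 35% |
|---|---|---|---|---|
| 0% | 5% | 5% | 5% | 5% |
| 10% | 15% | 9% | 6% | 5.5% |
| 20% | 21% | 18% | 12% | 8% |
| 30% | 23% | 21% | 17% | 13% |

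**With subject slopes allowed for.** With complete data and linear time, the random-slope F test equals a one-way ANOVA of per-subject slopes on 3 and 16 df. It rejected 4.3-5.5% of the time over all 12 times and 4.4-5.3% over days 7-84. Keeping 12 time categories and adding a random slope with a Satterthwaite F gave 3.7-4.5%. One-way ANOVA of log half-life gave 4.6-5.3%.

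**Versions in which the interaction is real.** On the raw scale the IV doses span 10 / 0.1 = 100-fold. With identical elimination and dose-proportional levels, the fall in µg/mL in group 4 is 100 times that in group 1, so the profiles cannot be parallel. Simulated rejection was 100%. With group 5 included on the log scale, the absorption phase bends its early profile; at an assumed absorption half-life of 0.5-3 days, rejection was again 100%.

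**The case against.** The strongest objection is that the model as worded is not the one tested above. The SAP speaks of group, of which there are five, and of concentration in µg/mL. In that form the interaction is real by design, so there is no true null to reject falsely. This stands, and it is why the type I error finding is limited to log concentration in the IV groups. The log version is a natural choice given the SAP's transformation rule, but it is not stated.

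It also stands that nothing depends on this model. It is optional, no elimination conclusion is drawn from it, between-arm comparisons are unpowered, and individual curves, half-life CVs and the population model will show between-subject variation directly. A reader might infer that the trial's pharmacokinetic conclusions are compromised. The documents do not support that.

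Two further inferences are tempting. One is to code time as a straight line with a random intercept only, which gives much larger error rates; the SAP refers to timepoints, so that is not the natural reading. The other is to project how much of group 1 would fall below the assay's quantification limit. Neither document states a limit. The protocol 6.5 projection, in which the starting dose "administered to 60 kg volunteer with a circulating volume of 5 L, would be expected to result in a peak concentration of" about 1.2 µg/mL, is 6 mg divided by a circulating volume of 5 L, whereas the ELISA measures serum. No percentage can be derived from this.

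The objection does not remove the defect in the test. Low power and parallel analyses do not correct this model's p-value, and the random intercept does not meet its stated purpose of handling within-subject correlation.

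**Conclusion.** The concern holds in a limited form. On log concentration in IV groups 1-4, a random-intercept-only interaction test has type I error of about 5-23% at a nominal 5%, for half-life CV 10-30% and residual CV 10-35%. At half-life CV 10% with residual CV 25% or more the inflation is negligible; with no half-life variation there is none. These sizes rest on assumed variances, balanced complete data, categorical time and a common 20.5-day median half-life.

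On the raw scale, or with group 5 included, a significant interaction is expected and is not evidence that elimination differs.

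The consequence is small. This is a cheap improvement to a secondary, optional analysis and does not threaten the trial's main results.

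**What to change.** Replace the SAP sentence with:

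> If this model is used, log concentration in IV groups 1-4 is modelled with group, time and group-by-time, with a random intercept and a random slope on time per subject, and the interaction is tested with a small-sample F test (Kenward-Roger or Satterthwaite). Group 5 is modelled separately. If the model does not converge, log terminal half-life from the NCA is compared across the IV groups by one-way ANOVA.

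The SAP should also say whether time is linear or categorical. Restricting the model to days 7-84 is optional: it avoids the early samples, where a straight line may fit poorly, but drops six of the twelve times.

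The cost is a few sentences and no new data. The drawback is that slopes are estimated from 5 subjects per group, so convergence may fail and power is modest. Power to detect a one-third shorter half-life in group 4:

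| Test | Residual CV 15%: half-life CV 20% / 30% | Residual CV 35%: half-life CV 20% / 30% |
|---|---|---|
| Linear slope, days 7-84 | 83% / 49% | 71% / 44% |
| 12 categories plus random slope | 45% / 20% | 38% / 18% |
| ANOVA of log half-life (fallback) | 80% / 46% | 65% / 39% |

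The fallback loses little power against the linear slope test. If the model is kept only as description, saying so and reporting no interaction p-value would also remove the problem.
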